6.11.2 Laboratory Data

The following laboratory tests will be performed at Screening and during discharge (or early termination).

QMD Ref: Worldwide-TMP-ST-006-4.0 Effective: 12Aug2019	Governing QMD: Worldwide-SOP-ST-001
Confidentiality Statement This document is the property of Worldwide Clinical Trials Inc. and may not be duplicated, copied, altered or removed from company without prior approval from Worldwide Quality Assurance or in compliance with Worldwide Standard Operating Procedures.	

Worldwide Clinical Trials Controlled Quality Management Document			
 WORLDWIDE CLINICAL TRIALS	Sponsor:	Opiant Pharmaceuticals	
	Protocol Number:	OPNT003-PK-002	

Hematology	Urinalysis	Serum Chemistry	Coagulation
Hemoglobin	Specific gravity	Total protein	Prothrombin time
Hematocrit	Glucose	Albumin	Activated partial thromboplastin time
Red blood cells	Bilirubin	Blood urea nitrogen	
Total white blood cells	Ketones	Creatinine	
Automated differential blood count	Blood	Alkaline Phosphatase	
Platelet count	pH	Alanine aminotransferase	
	Protein	Aspartate aminotransferase	
	Nitrite	Total bilirubin	
	Leukocyte esterase	Sodium	
		Potassium	
		Chloride	
		CO ₂	
		Calcium	
		Glucose	
		Total cholesterol	

Descriptive statistics of the observed values for Baseline and EOS/ET visit and change from Baseline (continuous data) to EOS/ET will be presented for each hematology, urinalysis, serum chemistry parameter and coagulation markers by treatment sequence and overall. Shift summaries of normal range indicators (Low, Normal and High) from Baseline to Discharge visit will be presented by treatment sequence.

All hematology, urinalysis, serum chemistry and coagulation markers data will be listed.

A separate listing of any out of range laboratory measurements recorded throughout the study will be presented.

All other laboratory data, including Viral Serology, Serum FSH, Pregnancy Test, and Urine Drug, Alcohol, Cotinine, Substance use and COVID-19 PCR Test will be listed only.

In Mock Shells: Tables 14.3.4.1 to 14.3.4.9, Listing 16.2.8.1 to 16.2.8.9

6.11.3 Vital Signs

All Vital signs except temperature will be tabulated for Baseline, 0.25 h, 0.5 h, 1 h, 2 h, 4 h, 8 h, 24 h and 48 h post-dose and the respective changes from Baseline, per treatment. Temperature will be tabulated for Baseline and EOS/ET and the change from Baseline, per treatment. In addition, vital signs values will be tabulated for Baseline, EOS/ET, and change from Baseline to EOS/ET by treatment sequence and overall.

Descriptive statistics for the following vital signs will be presented:

QMD Ref: Worldwide-TMP-ST-006-4.0 Effective: 12Aug2019	Governing QMD: Worldwide-SOP-ST-001
Confidentiality Statement	

This document is the property of Worldwide Clinical Trials Inc. and may not be duplicated, copied, altered or removed from company without prior approval from Worldwide Quality Assurance or in compliance with Worldwide Standard Operating Procedures.

Worldwide Clinical Trials Controlled Quality Management Document		
 WORLDWIDE CLINICAL TRIALS	Sponsor:	Opiant Pharmaceuticals

- Systolic blood pressure (mmHg)
- Diastolic blood pressure (mmHg)
- Pulse rate (beats/min)
- Respiration rate (breath/min)
- Body temperature (°Celsius)

Also, Shift tables in relation to investigator assessment i.e. Normal, Abnormal NCS (Not Clinically Significant), and Abnormal CS (Clinically Significant), from Baseline to each post-baseline visits will be presented. EOS/ET visit will be presented by Treatment sequence and all other post-baseline visits will be presented by treatment.

All vital sign data, including details of any clinically significant values will be listed.

In Mock Shells: Tables 14.3.5.1 and 14.3.5.2, Listing 16.2.8.10

6.11.4 Electrocardiogram Data

ECG values will be tabulated for Baseline, day 6, day 12 and EOS/ET, and change from Baseline to day 6 and 12, and change from Baseline to EOS by treatment sequence and overall. Parameters will be listed in the order given below and in units collected.

- Ventricular rate (bpm)
- PR Duration (ms)
- RR interval (ms)
- QRS Duration (ms)
- QT interval (ms)
- QTc interval (ms) [Fridericia's formula - QTcF]

Shift tables in relation to the overall interpretation i.e. Normal, Abnormal NCS, and Abnormal CS, from Baseline to each follow-up visit will be presented.

All ECG data, including details of any abnormalities, will be listed.

In Mock Shells: Table 14.3.6.1 and 14.3.6.2, Listing 16.2.8.11

6.11.5 Physical Examination

Shift in physical examination data (Normal, Abnormal NCS, Abnormal CS) from baseline to EOS/ET will be summarized by treatment sequence and overall.

QMD Ref: Worldwide-TMP-ST-006-4.0 Effective: 12Aug2019	Governing QMD: Worldwide-SOP-ST-001
Confidentiality Statement	

This document is the property of Worldwide Clinical Trials Inc. and may not be duplicated, copied, altered or removed from company without prior approval from Worldwide Quality Assurance or in compliance with Worldwide Standard Operating Procedures.

Worldwide Clinical Trials Controlled Quality Management Document		
 WORLDWIDE CLINICAL TRIALS	Sponsor: Protocol Number:	Opiant Pharmaceuticals OPNT003-PK-002

All data, including details of clinically significant findings will be listed.

In Mock Shells: Table 14.3.6.3, Listing 16.2.8.12

6.11.6 Nasal Passage Examination

Nasal passage examination results will be presented for Baseline, 5 minutes, 1, 8, 24 and 48 hour post-dose by treatment. Shift in results from Baseline to all post-dose measurements will be presented by treatment.

Nasal irritation will be determined on the following scale:

Nasal Irritation Scale

0 - Normal appearing mucosa, no bleeding

1 - Inflamed mucosa (erythema/edema), no bleeding

2 - Minor bleeding which stops within 1 minute

3 - Minor bleeding, taking 1-5 minutes to stop

4 - Substantial bleeding for 4-60 minutes, does not require medical intervention

5 - Ulcerated lesions, bleeding which requires medical intervention

A shift table for nasal irritation scale from Baseline to post-baseline time points will be presented.

All nasal passage examination data will be listed for the Safety Population.

In Mock Shells: Table 14.3.6.4.1 and 14.3.6.4.2, Listing 16.2.8.13

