^a Nasal passage examination on both nostrils will be performed at pre-dose, and at approximately 5 minutes (\pm 1 minute) and at 1 and 8 hours post-dose (\pm 15 minutes).

^b Nasal passage examination on both nostrils will be performed at approximately 24 hours post dose (\pm 30 minutes).

^c Nasal passage examination on both nostrils will be performed at approximately 48 hours post dose (\pm 30 minutes).

^d ECG assessment will be conducted at 20 (\pm 5 minutes) minutes, and at 1 (\pm 15 minutes) and 6 (\pm 15 minutes) hours post-dose.

^e Sitting (5 minutes) blood pressure, heart rate, respiration rate, and temperature.

^f Blood pressure, heart rate, respiration rate, pre-dose (within 30 minutes; sitting) and at approximately 15 and 30 minutes (supine), and at 1, 2, 4 and 8 (\pm 15 minutes; sitting) hours post-dose, after at least 5 minutes rest.

^g Blood pressure, heart rate, respiration rate, at approximately 24 hours (\pm 30 minutes; sitting) post-dose, after at least 5 minutes rest.

^h Blood pressure, heart rate, respiration rate, at approximately 48 hours (\pm 30 minutes; sitting) post-dose, after at least 5 minutes rest.

ⁱ Chemistry parameters include: total protein, albumin, blood urea nitrogen, creatinine, alkaline phosphatase, ALT, AST, total bilirubin, glucose, sodium, potassium, chloride, CO₂, total cholesterol, and calcium. Coagulation parameters include PT and aPTT.

^j CBC with differentials and platelet count will be performed.

^k Urinalysis includes: pH, specific gravity, blood, ketones, nitrites, glucose, bilirubin, leukocyte esterase, protein.

^l Urine toxicology screen for alcohol, opioids, cocaine, amphetamine/methamphetamine, benzodiazepines, barbiturates, THC, or methadone.

^m Pre-dose (within 15 mins), 2.5, 5, 7.5, 10, 15, 20, 30, 45 minutes and 1, 2, 3, 4, 6, 8, 12, 18 hours post-dose. Pre-dose blood sample will be collected within 15 minutes before dosing. Actual blood collection times can vary as follows: \pm 30 seconds for the 2.5, 5 & 7.5 samples, \pm 1 minute for the 10 to 30-minute samples, \pm 3 minutes for the 45 to 120-minute samples, and \pm 5 minutes for the 180 minute or greater samples.

ⁿ 24 (\pm 5 minutes) hours post dose.

^o 48 hours post dose (\pm 5 minutes). At discharge, collect sample after last blood draw prior to Final Discharge (or early termination) after the third dosing for clinical chemistry, coagulation markers and hematology.

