3.2 Safety Endpoints

Safety endpoints will include:

- Adverse events (AEs)
- Vital signs (heart rate, sitting blood pressure, and respiration rate)
- Electrocardiogram (ECG)
- Clinical laboratory changes
- Numerical rating scale (NRS) measuring acute nasal pain and nasal irritation (erythema, edema, and erosion) determined from the nasal passage examination following each nasal administration of study drug

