- TEAE by system organ class, preferred term and maximum severity, incidence. If a subject had multiple occurrences of the same PT within a treatment period, it is counted once with maximum severity under the PT; if a subject had multiple PTs within the SOC with different grades of maximum severity, it is counted once within each applicable severity grade within the SOC and Any TEAE categories.
- TEAE by system organ class, preferred term and closest relationship, incidence. If a subject had multiple occurrences of the same PT within a treatment period, it is counted once with closest relationship under the PT; if a subject had multiple PTs within the SOC with different grades of closest relationship, it is counted once within each applicable relationship category within the SOC and Any TEAE categories. Listing of Serious TEAEs (presented in the Table section of the appendices).
- Listing of Deaths (presented in the Table section of the appendices).
- Listing of Adverse events leading to Early Withdrawal (presented in the Table section of the appendices).

All AEs will be separately listed.

In Mock Shells: Tables 14.3.1.1 to 14.3.1.8, Tables 14.3.2.1 to 14.3.2.3, Listing 16.2.7.1

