14.3.4.8	Urinalysis Data, Shift Summary - Safety Population	IP	16.2.8.1
14.3.4.9	Out of Range Laboratory Data – Safety Population	IP	-
14.3.5	Vital Signs and Physical Examination		
14.3.5.1	Vital Signs, Descriptive Statistics – Safety Population	IP	-
14.3.5.2	Vital Signs, Shift Summary – Safety Population	IP	-
14.3.6	Other Safety		
14.3.6.1	12 Lead ECG, Descriptive Statistics - Safety Population	IP	-

QMD Ref: Worldwide-TMP-ST-008-2.0 Effective: 12Aug2019	Governing QMD: Worldwide-SOP-ST-001
Confidentiality Statement	
This document is the property of Worldwide Clinical Trials Inc. and may not be duplicated, copied, altered or removed from company without prior approval from Worldwide Quality Assurance or in compliance with Worldwide Standard Operating Procedures.	

Worldwide Clinical Trials Controlled Quality Management Document			
 WORLDWIDE CLINICAL TRIALS	Sponsor:	Opiant Pharmaceuticals	
	Protocol Number:	OPNT003-PK-002	
POST DATABASE LOCK STATISTICAL ANALYSIS PLAN ADDENDUM			

Table Number	Table Title	Validation Method	Shell Number (if repeat)
14.3.6.2	12 Lead ECG, Shift Summary - Safety Population	IP	-
14.3.6.3	Physical Examination Data, Shift Summary - Safety Population	IP	-
14.3.6.4.1	Nasal Cavity Examination Data, Descriptive Statistics - Safety Population	IP	-
14.3.6.4.2	Nasal Cavity Examination Data, Shift Summary - Safety Population	IP	-
14.3.6.5	Numerical Rating Scale Data, Descriptive Statistics - Safety Population	IP	-
14.3.6.6	Brief Smell Identification Score Data, Descriptive Statistics - Safety Population	IP	-
14.3.7	Concomitant Medication		
	Not Applicable		
14.4	PK Tables		
14.4.1	Descriptive Statistics for Concentration-Time Data of Nalmefene after IN Administration of 3 mg Nalmefene HCl in One Nostril (T1, Treatment A), 3 mg (6 mg Total Dose) Nalmefene HCl in Each Nostril (Treatment B, T2), and 6 mg Nalmefene HCl in One Nostril (Treatment C, T3) – PK Evaluation Population	IP	-
14.4.2	Plasma PK Parameters of Nalmefene after IN Administration of 3 mg Nalmefene HCl in One Nostril (T1, Treatment A), 3 mg (6 mg Total Dose) Nalmefene HCl in Each Nostril (Treatment B, T2), and 6 mg	IP	-

QMD Ref: Worldwide-TMP-ST-008-2.0 Effective: 12Aug2019	Governing QMD: Worldwide-SOP-ST-001
Confidentiality Statement	

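### The planned nasal tables report irritation exam by exam, so they generally do not show how many distinct subjects had irritation or bleeding after each regimen; a worst post-dose grade would.

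*SAP*

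**What the plan says.** SAP 3.2 lists nasal irritation among the safety endpoints, "determined from the nasal passage examination following each nasal administration of study drug".

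SAP 6.11.6 sets out the summaries: "Nasal passage examination results will be presented for Baseline, 5 minutes, 1, 8, 24 and 48 hour post-dose by treatment". It continues: "Shift in results from Baseline to all post-dose measurements will be presented by treatment". For the 0 to 5 irritation scale it adds: "A shift table for nasal irritation scale from Baseline to post-baseline time points will be presented". Subject-level results go to Listing 16.2.8.13: "All nasal passage examination data will be listed for the Safety Population".

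The table list attached to the post-lock addendum keeps two nasal tables: 14.3.6.4.1 (descriptive statistics) and 14.3.6.4.2, now titled "Nasal Cavity Examination Data, Shift Summary - Safety Population". For these two tables the addendum adds categories for missing exams, corrects the listing references and changes one title. It mentions no worst-grade summary.

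The Protocol's Schedule of Events has both sides examined: "Nasal passage examination on both nostrils will be performed at pre-dose, and at approximately 5 minutes". SAP 6.11.6 does not say how the two nostril grades become one result.

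For AEs, SAP 6.11.1 does reduce repeats to one record. A subject with the same preferred term more than once in a treatment period is handled as follows: "it is counted once with maximum severity under the PT".

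**The concern.** Local tolerability is the safety question most specific to this product, because the regimens differ in the number of sprays and in how they are divided between nostrils. The simplest result a reader would want is how many subjects, out of those given each regimen, had irritation or bleeding at any exam after the dose. The planned nasal tables give five separate counts per regimen and nothing that links a subject's exams to each other. One subject with irritation at three exams and three subjects with irritation at one exam each contribute the same total. Two regimens with the same exam-by-exam tables could therefore differ in the number of subjects affected, and a reader of the tables alone could not tell.

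**Working it through.** The documents give no planned or observed figure for nasal irritation, so there is nothing to reproduce. The check is whether the planned counts determine the quantity of interest.

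**Inputs**
- Post-dose exams per regimen: 5 (SAP 6.11.6).
- Subjects per regimen: 24 planned, since every subject receives all three treatments (SAP 5).
- Counts of subjects above period Baseline at each exam, c1 to c5: assumed, for illustration only.

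**Formula.** The number of distinct subjects with a finding at one or more exams is the size of the union of five sets with sizes c1 to c5. From the sizes alone:

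- lower bound = max(c1, …, c5), when every affected subject is among those affected at the busiest exam;
- upper bound = min(24, c1 + … + c5), when overlap is as small as possible.

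**Results with assumed counts**

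| Counts at 5 min, 1, 8, 24, 48 h | Lower | Upper | Range of 24 |
|---|---|---|---|
| 2, 3, 2, 1, 1 | 3 | 2+3+2+1+1 = 9 | 12.5% to 37.5% |
| 1, 1, 1, 1, 1 | 1 | 5 | 4.2% to 20.8% |
| 3, 3, 3, 3, 3 | 3 | 15 | 12.5% to 62.5% |
| 6, 4, 2, 1, 0 | 6 | 13 | 25.0% to 54.2% |
| 3, 0, 0, 0, 0 | 3 | 3 | 12.5% (exact) |

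The count is exact only in special cases, such as no findings at all or findings at a single exam.

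**How plausible the upper end is.** Take 3 of 24 (12.5%) at every exam. If the five exams of one subject were independent, the expected number affected would be 24 × (1 − 0.875^5) = 24 × 0.487 = 11.7. Repeated exams of the same mucosa after one dose are more likely to be positively associated. That association would put the expected number below 11.7, towards the lower bound of 3. The upper bound of 15 needs fifteen subjects, each abnormal at exactly one exam.

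**Does the shift table resolve it?** A shift table splits each exam's counts by Baseline grade. That can narrow the range, but it still pairs each exam with Baseline only and never one post-dose exam with another. If most subjects start at grade 0, it narrows very little.

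**Other routes in the plan.** The Protocol synopsis says that examination of the nasal mucosa is one way AEs are assessed. Findings recorded as AEs would be counted per subject and treatment in Tables 14.3.1.2 and 14.3.1.7. Those tables use preferred term and AE severity rather than the irritation scale, and no rule makes every grade of 1 or more an AE. The listing covers at most 24 × 3 = 72 subject-periods, so the count can be derived from it.

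**The case against.** The strongest reply is that nothing here is wrong. SAP 3.2 asks for irritation after each administration and SAP 6.11.6 reports it by treatment at every scheduled exam, with shifts. It does not promise one grade per administration. Time-point display is also how the SAP treats its other scheduled measurements (vital signs, ECG, pain rating, smell test), whereas the maximum-severity rule for AEs serves to avoid counting repeated events twice. All of this stands. A reader might infer that the plan contradicts its own endpoint; the documents do not support that.

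The reply can add that the data are all listed, that 72 subject-periods are few, that SAP 6 allows further tables if justified in the study report, and that some exam findings will reach the AE tables. This also stands. It means the gap is one of summary and not of information. It does not close the gap: a listing leaves the derivation undefined, and the AE tables catch only findings that someone recorded as AEs.

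The mock shells are not among the documents, so a worst-grade row there cannot be excluded. Neither the SAP text nor the addendum's list of shell changes mentions one.

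Finally, a reader might infer from the bounds that a 25 to 50 percentage-point difference between regimens (37.5 − 12.5 or 62.5 − 12.5) could go unseen. That needs no overlap between exams under one regimen and complete overlap under the other, on invented counts. It is an extreme bound, and the documents hold no irritation data that make it likely.

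**Conclusion.** The point holds as a limited gap in the planned summaries. The nasal tables described in the SAP and addendum generally bound, but do not give, the number of distinct subjects affected after each regimen. For the assumed counts 2, 3, 2, 1 and 1 the bound is 3 to 9 of 24; the likely value lies nearer the lower end if exams are positively associated.

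This rests on 24 evaluable subjects per regimen, on assumed counts, and on the unseen shells containing no worst-grade row. The time-point tables are correct as far as they go and should stay. No pharmacokinetic conclusion is affected. The change is worth making because safety and tolerability is the stated secondary objective, the data are already collected, and the cost is small.

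**What to change.** Add to SAP 6.11.6:

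> For each subject and treatment, the worst nasal irritation grade over the scheduled exams from 5 minutes to 48 hours will be derived, using the higher grade of the two nostrils at each exam. The period Baseline will be derived in the same way. Tables 14.3.6.4.1 and 14.3.6.4.2 will also show, by treatment, the worst post-dose grade, its shift from the period Baseline, the number (%) of subjects whose worst grade exceeds Baseline, and the number (%) with any bleeding grade (2 or higher).

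With this:
- Keep the time-point rows.
- Footnote subjects with a missed exam, whose worst grade is taken over the exams done.
- State that the 48-hour exam after the third dose belongs to Period 3. It falls on Day 15, which SAP 6.2.1 maps to the end-of-study visit with no period.
- Reconcile the scale. Grade 3 covers bleeding of 1 to 5 minutes and grade 4 bleeding of 4 to 60 minutes, so they overlap from 4 to 5 minutes and the worst grade is ambiguous there.
- If the change is made after database lock, label it as such and justify it in the study report. The addendum already revised the ECG tables after lock in this way.

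The cost is one derived record per subject and period, one extra block in two existing tables, and the nostril and scale rules above. No new data are needed. The downside is a little programming, and a worst grade that may be understated where an exam was missed.

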6.11.7 Numerical Rating Scale

Descriptive statistics of NRS data at Baseline, 15 minutes and 60 minutes post-dose will be presented by treatment and overall. A listing of all NRS data will be provided for the Safety Population.

In Mock Shells: Table 14.3.6.5, Listing 16.2.8.14

6.11.8 Smell Test

Descriptive statistics of smell test score for Baseline and post-baseline time points will be presented by treatment and overall. Additionally, all smell test data will be listed for the Safety Population.

QMD Ref: Worldwide-TMP-ST-006-4.0 Effective: 12Aug2019	Governing QMD: Worldwide-SOP-ST-001
Confidentiality Statement	
This document is the property of Worldwide Clinical Trials Inc. and may not be duplicated, copied, altered or removed from company without prior approval from Worldwide Quality Assurance or in compliance with Worldwide Standard Operating Procedures.	

Worldwide Clinical Trials Controlled Quality Management Document		
 WORLDWIDE CLINICAL TRIALS	Sponsor:	Opiant Pharmaceuticals
	Protocol Number:	OPNT003-PK-002

In Mock Shells: Table 14.3.6.6, Listing 16.2.8.15

7 CHANGES TO PLANNED PROTOCOL ANALYSIS

During the analysis and reporting process, any deviations from the statistical analysis plan will be described and justified in writing in the CSR.

QMD Ref: Worldwide-TMP-ST-006-4.0 Effective: 12Aug2019	Governing QMD: Worldwide-SOP-ST-001
Confidentiality Statement This document is the property of Worldwide Clinical Trials Inc. and may not be duplicated, copied, altered or removed from company without prior approval from Worldwide Quality Assurance or in compliance with Worldwide Standard Operating Procedures.	

Worldwide Clinical Trials Controlled Quality Management Document		
 WORLDWIDE CLINICAL TRIALS	Sponsor:	Opiant Pharmaceuticals
	Protocol Number:	OPNT003-PK-002

9 LIST OF TABLES, FIGURES AND LISTINGS

The following table includes details of the tables, figures and listings to be included within each section of the electronic common technical document (eCTD). The eCTD section is shown in bold. The following validation methods maybe used:

- Independent programming of numbers and manual review of format (IP)
- Independent programming by statistician of numbers and manual review of format (Stat IP)
- Manual review (MR)
- Code review (CR)

Table Number	Table Title	Validation Method	Shell Number (if repeat)
Items in bold are not table titles but references to the section headings within eCTD.			
14.1	Demographics Data		
14.1.1	Disposition		
14.1.1	Subject Disposition, Analysis Populations – All Randomized Subjects	IP	-
14.1.2	Demographics		
14.1.2.1	Summary of Demographics - Safety Population	IP	-
14.1.2.2	Summary of Demographics - PK Population	IP	14.1.2.2
14.1.3	Baseline Characteristics		
	Not Applicable		
14.2	Efficacy Data		
	Not Applicable		
14.3	Safety Data		
14.3.1	Displays of Adverse Events		
14.3.1.1	Overall Summary of Treatment Emergent Adverse Events (TEAEs) – Safety Population	IP	-
14.3.1.2	TEAEs By Primary System Organ Class and Preferred Term – Safety Population	IP	-
14.3.1.3	Treatment Related TEAEs By Primary System Organ Class and Preferred Term – Safety Population	IP	14.3.1.2
14.3.1.4	Serious TEAEs By Primary System Organ Class and Preferred Term – Safety Population	IP	14.3.1.2
14.3.1.5	Related Serious TEAEs by Primary System Organ Class and Preferred Term – Safety Population	IP	14.3.1.2
14.3.1.6	Treatment Emergent Adverse Events leading to Early Withdrawal by SOC and PT – Safety Population	IP	14.3.1.2

QMD Ref: Worldwide-TMP-ST-006-4.0 Effective: 12Aug2019

Governing QMD: Worldwide-SOP-ST-001

Confidentiality Statement

This document is the property of Worldwide Clinical Trials Inc. and may not be duplicated, copied, altered or removed from company without prior approval from Worldwide Quality Assurance or in compliance with Worldwide Standard Operating Procedures.

Worldwide Clinical Trials Controlled Quality Management Document			
 WORLDWIDE CLINICAL TRIALS	Sponsor:	Opiant Pharmaceuticals	
	Protocol Number:	OPNT003-PK-002	

Table Number	Table Title	Validation Method	Shell Number (if repeat)
14.3.1.7	Treatment Emergent Adverse Events by SOC, PT and Maximum Severity - Safety Population	IP	-
14.3.1.8	Treatment Emergent Adverse Events by SOC, PT and Closest Relationship - Safety Population	IP	-
14.3.2	Listings of Deaths, Other Serious and Significant Adverse Events		
14.3.2.1	Listing of SAEs – Safety Population	IP	16.2.7.1
14.3.2.2	Listing of Deaths – Safety Population	IP	16.2.7.1
14.3.2.3	Listing of TEAEs Leading to Early Withdrawal – Safety Population	IP	16.2.7.1
14.3.3	Narratives of Deaths, Other Serious and Certain Other Significant Adverse Events		
14.3.4	Abnormal Laboratory Values		
14.3.4.1	Hematology Data, Descriptive Statistics - Safety Population	IP	-
14.3.4.2	Clinical Chemistry Data, Descriptive Statistics - Safety Population	IP	14.3.4.1
14.3.4.3	Coagulation Data, Descriptive Statistics - Safety Population	IP	14.3.4.1
14.3.4.4	Urinalysis Data, Descriptive Statistics - Safety Population	IP	14.3.4.1
14.3.4.5	Hematology Data, Shift Summary - Safety Population	IP	-
14.3.4.6	Clinical Chemistry Data, Shift Summary - Safety Population	IP	14.3.4.5
14.3.4.7	Clinical Chemistry Data, Shift Summary - Safety Population	IP	14.3.4.5
14.3.4.8	Urinalysis Data, Shift Summary - Safety Population	IP	16.2.8.1
14.3.4.9	Listing of Out of Range Laboratory Data – Safety Population	IP	-
14.3.5	Vital Signs and Physical Examination		
14.3.5.1	Vital Signs, Change from Baseline – Safety Population	IP	-
14.3.5.2	Vital Signs, Shift Summary – Safety Population	IP	-
14.3.6	Other Safety		
14.3.6.1	12 Lead ECG, Descriptive Statistics - Safety Population	IP	-
14.3.6.2	12 Lead ECG, Shift Summary - Safety Population	IP	-
14.3.6.3	Physical Examination Data, Shift from Baseline - Safety Population	IP	-

QMD Ref: Worldwide-TMP-ST-006-4.0 Effective: 12Aug2019

Governing QMD: Worldwide-SOP-ST-001

Confidentiality Statement

This document is the property of Worldwide Clinical Trials Inc. and may not be duplicated, copied, altered or removed from company without prior approval from Worldwide Quality Assurance or in compliance with Worldwide Standard Operating Procedures.

Worldwide Clinical Trials Controlled Quality Management Document			
 WORLDWIDE CLINICAL TRIALS	Sponsor:	Opiant Pharmaceuticals	
	Protocol Number:	OPNT003-PK-002	

Table Number	Table Title	Validation Method	Shell Number (if repeat)
14.3.6.4.1	Nasal Cavity Examination Data, Descriptive Statistics - Safety Population	IP	-
14.3.6.4.2	Nasal Cavity Examination Data, Shift from Baseline - Safety Population	IP	-
14.3.6.5	Numerical Rating Scale Data, Descriptive Statistics - Safety Population	IP	-
14.3.6.6	Brief Smell Identification Score Data, Descriptive Statistics - Safety Population	IP	-
14.3.7	Concomitant Medication		
	Not Applicable		
14.4	PK Tables		
14.4.1	Descriptive Statistics for Concentration-Time Data of Nalmefene after IN Administration of 3 mg Nalmefene HCl in One Nostril (T1, Treatment A), 3 mg (6 mg Total Dose) Nalmefene HCl in Each Nostril (Treatment B, T2), and 6 mg Nalmefene HCl in One Nostril (Treatment C, T3) – PK Evaluation Population	IP	-
14.4.2	Plasma PK Parameters of Nalmefene after IN Administration of 3 mg Nalmefene HCl in One Nostril (T1, Treatment A), 3 mg (6 mg Total Dose) Nalmefene HCl in Each Nostril (Treatment B, T2), and 6 mg Nalmefene HCl in One Nostril (Treatment C, T3) – PK Evaluation Population	IP	-
14.4.3	Plasma PK Partial AUCs of Nalmefene after IN Administration of 3 mg Nalmefene HCl in One Nostril (T1, Treatment A), 3 mg (6 mg Total Dose) Nalmefene HCl in Each Nostril (Treatment B, T2), and 6 mg Nalmefene HCl in One Nostril (Treatment C, T3) – PK Population	IP	-
14.4.4	Plasma Dose-Normalized Parameters of Nalmefene after IN Administration of 3 mg Nalmefene HCl in One Nostril (T1, Treatment A), 3 mg (6 mg Total Dose) Nalmefene HCl in Each Nostril (Treatment B, T2), and 6 mg Nalmefene HCl in One Nostril (Treatment C, T3) – PK Population	IP	-
14.4.5	Dose-Normalized Plasma PK Partial AUCs of Nalmefene after IN Administration of 3 mg Nalmefene	IP	-

QMD Ref: Worldwide-TMP-ST-006-4.0 Effective: 12Aug2019	Governing QMD: Worldwide-SOP-ST-001
Confidentiality Statement	

This document is the property of Worldwide Clinical Trials Inc. and may not be duplicated, copied, altered or removed from company without prior approval from Worldwide Quality Assurance or in compliance with Worldwide Standard Operating Procedures.

Worldwide Clinical Trials Controlled Quality Management Document			
 WORLDWIDE CLINICAL TRIALS	Sponsor:	Opiant Pharmaceuticals	
	Protocol Number:	OPNT003-PK-002	

Table Number	Table Title	Validation Method	Shell Number (if repeat)
	HCl in One Nostril (T1, Treatment A), 3 mg (6 mg Total Dose) Nalmefene HCl in Each Nostril (Treatment B, T2), and 6 mg Nalmefene HCl in One Nostril (Treatment C, T3) – PK Population		
14.4.6	Statistical Analysis of the Natural Log-Transformed, Dose-Normalized Exposure Parameters of Nalmefene Comparing 6 mg Nalmefene Hydrochloride in One Nostril (Treatment C, T3, Test) and 3 mg Nalmefene Hydrochloride in One Nostril (Treatment A, T1, Reference) – PK Evaluation Population	IP	-
14.4.7	Statistical Analysis of the Natural Log-Transformed, Dose-Normalized Exposure Parameters of Nalmefene Comparing 3 mg Nalmefene Hydrochloride in Each Nostril (6 mg Total Dose, Treatment B, T2, Test) and 3 mg Nalmefene Hydrochloride in One Nostril (Treatment A, T1, Reference) – PK Evaluation Population	IP	-
14.4.8	Statistical Analysis of the Natural Log-Transformed, Dose-Normalized Exposure Parameters of Nalmefene Comparing 3 mg Nalmefene Hydrochloride in Each Nostril (6 mg Total Dose, Treatment B, T2, Test) and 6 mg Nalmefene Hydrochloride in One Nostril (Treatment C, T3, Reference) – PK Evaluation Population	IP	-
14.5	PD Tables		
14.6	Other Data		

QMD Ref: Worldwide-TMP-ST-006-4.0 Effective: 12Aug2019	Governing QMD: Worldwide-SOP-ST-001
Confidentiality Statement	

This document is the property of Worldwide Clinical Trials Inc. and may not be duplicated, copied, altered or removed from company without prior approval from Worldwide Quality Assurance or in compliance with Worldwide Standard Operating Procedures.

Worldwide Clinical Trials Controlled Quality Management Document			
 WORLDWIDE CLINICAL TRIALS	Sponsor:	Opiant Pharmaceuticals	
	Protocol Number:	OPNT003-PK-002	

Figure Number	Figure Title	Validation Method	Shell Number (if repeat)
14.4.1	Nalmefene Concentration-Time Data, Mean Profiles on Linear and Semi-Logarithmic Scales after Intranasal (IN) Administrations of 3 mg Nalmefene Hydrochloride in One Nostril (T1), 2 x 3 mg Nalmefene Hydrochloride in Each Nostril (6 mg Total Dose, T2), and 6 mg Nalmefene Hydrochloride in One Nostril (T3) – PK Evaluation Population	IP	-
14.4.2	Nalmefene Concentration-Time Data, All Subject Profiles on Linear and Semi-Logarithmic Scales after Intranasal (IN) Administrations of 3 mg Nalmefene Hydrochloride in One Nostril (T1), 2 x 3 mg Nalmefene Hydrochloride in Each Nostril (6 mg Total Dose, T2), and 6 mg Nalmefene Hydrochloride in One Nostril (T3) – PK Evaluation Population	IP	-
14.4.3	Nalmefene Concentration-Time Data, Individual Profiles on Linear and Semi-Logarithmic Scales after Intranasal (IN) Administrations of 3 mg Nalmefene Hydrochloride in One Nostril (T1), 2 x 3 mg Nalmefene Hydrochloride in Each Nostril (6 mg Total Dose, T2), and 6 mg Nalmefene Hydrochloride in One Nostril (T3) – PK Evaluation Population	IP	-
14.4.4	Concentration-Time Profiles for Nalmefene with Linear Regression for Estimating the Terminal Elimination Rate - PK Evaluation Population	IP	-

QMD Ref: Worldwide-TMP-ST-006-4.0 Effective: 12Aug2019	Governing QMD: Worldwide-SOP-ST-001
Confidentiality Statement	

This document is the property of Worldwide Clinical Trials Inc. and may not be duplicated, copied, altered or removed from company without prior approval from Worldwide Quality Assurance or in compliance with Worldwide Standard Operating Procedures.

Worldwide Clinical Trials Controlled Quality Management Document			
 WORLDWIDE CLINICAL TRIALS	Sponsor:	Opiant Pharmaceuticals	
	Protocol Number:	OPNT003-PK-002	

Listing Number	Listing Title	Validation Method	Shell Number (if repeat)
16.2	Subject Data Listings		
16.2.1	Discontinued Subjects		
16.2.1.1	Subject Disposition – All Randomized Subjects	IP	-
16.2.2	Protocol Deviations		
16.2.2.1	Protocol Deviations – Safety Population	IP	-
16.2.3	Subjects Excluded from the Efficacy Analyses		
16.2.3.1	Analysis Populations – All Randomized Subjects	IP	-
16.2.4	Demographic Data		
16.2.4.1	Demographic Data – Safety Population	IP	-
16.2.4.2	Medical History – Safety Population	IP	-
16.2.4.3	Prior and Concomitant Medications - Safety Population	IP	-
16.2.5	Compliance and / or Drug Concentration Data		
16.2.5.1	Exposure Data – Safety Population	IP	-
16.2.6	Individual Efficacy Response Data		
16.2.6.1	Nalmefene Concentration-Time Data Listing – Safety Population	IP	-
16.2.6.2	Terminal Elimination Rate of Nalmefene in Plasma for Individual Subjects – PK Evaluation Population	IP	-
16.2.6.3	PK Output Text – PK Evaluation Population	IP	-
16.2.6.4	SAS Output Text (ANOVA) – PK Evaluation Population	IP	-
16.2.7	Adverse Event Listings		
16.2.7.1	Adverse Event Data – Safety Population	IP	-
16.2.8	Individual Laboratory Measurements and Other Safety		
16.2.8.1	Hematology Data – Safety Population	IP	-
16.2.8.2	Serum Chemistry Data – Safety Population	IP	16.2.8.1
16.2.8.3	Coagulation Data – Safety Population	IP	16.2.8.1
16.2.8.4	Urinalysis Data – Safety Population	IP	16.2.8.1
16.2.8.5	Drug and Alcohol Screen – Safety Population	IP	-
16.2.8.6	Serology Data – Safety Population	IP	16.2.8.5
16.2.8.7	Pregnancy Test Data – Safety Population	IP	-
16.2.8.8	Substance Use Data - Safety Population	IP	-

QMD Ref: Worldwide-TMP-ST-006-4.0 Effective: 12Aug2019	Governing QMD: Worldwide-SOP-ST-001
Confidentiality Statement	

